### **Exclusion Criteria**

1. Lack of informed consent
2. Continuous neuromuscular blockade at enrollment
3. Known pregnancy
4. Currently receiving ECMO therapy
5. Chronic respiratory failure defined as PaCO2 > 60 mm Hg in the outpatient setting
6. Home mechanical ventilation (non-invasive ventilation or via tracheotomy) except for CPAP/BIPAP used solely for sleep-disordered breathing
7. Actual body weight exceeding 1 kg per centimeter of height
8. Severe chronic liver disease defined as a Child-Pugh score of 12-15 (Appendix A2)
9. Bone marrow transplantation within the last 1 year

10. Expected duration of mechanical ventilation < 48 hours
11. Decision to withhold life-sustaining treatment; except in those patients committed to full support except cardiopulmonary resuscitation
12. Moribund patient not expected to survive 24 hours; if CPR provided, assess for moribund status  $\geq 6$  from CPR conclusion
13. Diffuse alveolar hemorrhage from vasculitis
14. Burns > 70% total body surface
15. Unwillingness to utilize the ARDS Network 6 ml/kg IBW ventilation protocol
16. Previous hypersensitivity or anaphylactic reaction to cisatracurium
17. Neuromuscular conditions that may potentiate neuromuscular blockade and/or impair spontaneous ventilation (Appendix A2)
18. Neurologic conditions undergoing treatment for intracranial hypertension
19. Enrollment in an interventional ARDS trial with direct impact on neuromuscular blockade and PEEP
20. PaO2/FiO2 (if available) >200 after meeting inclusion criteria and before randomization *Oxygenation may improve during the 48 hour enrollment window. This exclusion criterion ensures that patients with mild ARDS are not included in the study.*
21. Endotracheal ventilation for greater than 120 hours (5 days)
22. Patient has completed lung transplant evaluation and has been officially listed for lung transplant by UNOS

**Randomization and Study Initiation Time Window:** All patients must be enrolled and randomized within 48 hours of meeting inclusion criteria. After randomization, the low tidal volume protocol must be initiated within two hours (if not already being used). In the intervention arm, deep sedation followed by neuromuscular blockade must be initiated within four hours of randomization.

**Efficacy:** The primary outcome is all-cause mortality prior to discharge home before day 90.

1. **Secondary outcomes:**
  1. ICU acquired weakness
  2. IL-6 levels (plasma)
  3. Hospital mortality to day 28
  4. Ventilator free days to day 28
  5. Organ failure free days to day 28
  6. ICU-free days at day 28
  7. Hospital-free days at day 28
  8. Physiologic measures
  9. Long term outcome assessments
  10. Use of rescue procedures

11. Paralysis recall, in-hospital
12. Supraventricular tachycardia and new onset atrial fibrillation

**Sample Size/Interim Monitoring:**

1. With a 35% mortality rate in the control arm and 27% mortality rate in the intervention arm, the maximum required total sample size is 1408 subjects.
2. The principal analysis will be intent-to-treat, based upon randomization assignment.
3. Trial progress will be evaluated by an independent Data and Safety Monitoring Board (DSMB) to determine if the study should stop for superiority of either Active or Control therapy. There will be two interim analyses and a final analyses conducted when approximately each successive 1/3 of the patients have been enrolled.

### **3 TRIAL DESCRIPTION**

#### **3.1 BACKGROUND**

[figure not shown]
In 2010, the ACURASYS trial reported early neuromuscular blockade (also called skeletal muscle relaxant or muscle relaxant) administration improved adjusted survival for moderate to severe ARDS in a 340 patient trial conducted in 20 French ICUs.[2] While intriguing, this approach has not been widely adopted in the U.S., and key limitations exist. First, the trial was underpowered. Mortality benefit was noted only after statistical adjustment; crude 90d mortality did not differ. Control mortality was also lower than predicted (though higher than many recent ARDS trials)[3, 4] and the authors concluded “given the observed mortality in our placebo group, the current study was underpowered”. Second, the mechanism responsible for the improvement in outcome with neuromuscular blockade is unclear. One possible explanation is that neuromuscular blockade results in improvement in patient-ventilator asynchrony with subsequent reduction in ventilator-induced lung injury and inflammation. Third, assessment of a known side effect of the intervention, muscle paresis, has been criticized as inadequate. As a result of these concerns, the critical care community has collectively recommended another phase III clinical trial to definitively test the safety and efficacy of neuromuscular blockade in patients with ARDS.[5, 6]

#### **3.2 NEUROMUSCULAR BLOCKADE – POTENTIAL BENEFITS AND MECHANISMS**

One of the earliest ARDS Network trials demonstrated that low tidal volume ventilation led to an absolute reduction in mortality of 9%.[7] This ventilator strategy presumably reduced ventilator induced lung injury by avoiding alveolar over distension. Recent ARDS studies have examined whether ventilatory strategies such as high positive end expiratory pressure (PEEP) or high frequency oscillation may improve outcome. All of these trials have focused on adjusting the ventilator portion of the patient-ventilator interface. Therapies directed at reducing patient’s metabolic demands and improving the patient’s ability to interface with the ventilator, may also attenuate ventilator induced lung injury. Neuromuscular blockade may improve the patient

component of the patient-ventilator interface. Oxygen consumption of respiratory muscles normally represents only 1%-3% of cardiac output. Due to the decreased pulmonary compliance in ARDS, the work of breathing escalates and can constitute as much as 24% of the increased cardiac output[8]. These increases in cardiac output and blood flow across an injured pulmonary vasculature can generate higher filtration pressures and promote the formation of lung edema. By removing the ability of the respiratory muscles to contract, neuromuscular blockade reduces the oxygen consumption of these muscles, which in turn reduces cardiac output directed towards these muscles, increases the mixed venous partial pressure of oxygen, and can increase the partial pressure of oxygen in arterial blood. These same reductions in cardiac output diminish the volume of blood flow through the pulmonary capillaries, decrease the pulmonary vascular pressure gradient, and the accumulation of alveolar fluid. Vigorous expiratory effort can also result in alveolar collapse and reduced end-expiratory lung volumes. By preventing active expiration, neuromuscular blockade may create a more homogenous distribution of PEEP and tidal volumes, preventing barotrauma/volutrauma and “atelectrauma” resulting in less ventilator-induced lung injury[5] (See Figure 1).

**Figure 1**

### 3.3 NEUROMUSCULAR BLOCKADE – POTENTIAL HARMS

In the recent past, neuromuscular blockade was commonly used for ventilated patients with acute respiratory failure.[9] However, with its increased utilization, neuromuscular blockade was

implicated in the development of a severe and persistent neuromuscular weakness[10], though this association has been recently challenged[11]. Due to the concerns for these long term debilitating side effects combined with the availability of more efficacious sedative agents, the prolonged use of neuromuscular blocking agents for critically ill patients who require mechanical ventilation diminished over time.

### 3.4 RECENT FRENCH CLINICAL TRIALS

Based on the rationale outlined above, Papazian and colleagues examined the efficacy of neuromuscular blockade for ARDS. Their first study was a randomized controlled trial to determine the effects of 48 hours of neuromuscular blockade on gas exchange in patients with severe ARDS[12]. All patients were heavily sedated to a Ramsay score of six before randomization. Patients randomized to neuromuscular blockade demonstrated significant improvements in PaO2/FiO2 ratio during the first five days of their ICU course when compared to placebo. A second study evaluated the effects of neuromuscular blockade on pulmonary and systemic markers of inflammation in patients with ARDS[13]. All patients underwent a bronchoalveolar lavage (BAL) before randomization and at 48 hours. Neuromuscular blockade resulted in a decrease in IL-1 $\beta$ , IL-6, and IL-8 levels in the BAL fluid at 48 hours. There was also a significant decrease in serum concentrations of IL-6 and IL-8 in the patients who received neuromuscular blockade. Similar to their first study, patients who received neuromuscular blockade had a significant improvement in their oxygenation. Their third and most prominent study (ACURASYS), as noted above, showed decreased mortality with early neuromuscular blockade [2].

### 3.5 CURRENT PRACTICE IN PETAL SITES AND CLINICAL EQUIPOISE

To determine the utilization of neuromuscular blockade for patients with moderate to severe ARDS, we surveyed the principal investigators of the current PETAL network hospitals. Overall, 35 investigators answered the survey; representing all 12 PETAL sites. Only 11% of investigators stated that continuous neuromuscular infusions were commonly used for ARDS patients with a PaO2/FiO2 < 150 at their hospitals. In this survey, commonly was defined as between 80-100% of patients. The vast majority of these investigators (94%) were confident they would be able to randomize ARDS patients with a PaO2/FiO2 < 150 to a neuromuscular blockade protocol. Similarly, 100% of investigators would be able to follow a neuromuscular blockade protocol in the intervention arm of the study and enforce no routine use of neuromuscular blockade in the control arm.

These survey results demonstrate that neuromuscular blockade is uncommonly used for ARDS patients with a PaO2/FiO2 < 150, and that PETAL sites would be able to effectively perform a randomized study of neuromuscular blockade for ARDS patients with a PaO2/FiO2 < 150.

### 3.6 EARLY NEUROMUSCULAR BLOCKADE FOR ARDS NEEDS REEVALUATION

Despite the encouraging results of the Papazian studies, there are several compelling reasons why the PETAL Network should perform a second study of early neuromuscular blockade for ARDS. First and foremost, the pulmonary and critical care community has clearly learned that clinical trials often require replication and validation before the efficiency of a therapy is proven. In a review of 39 highly cited positive randomized clinical trials, the results were replicated in less than 50% of subsequent studies[14]. Relevant to critical care, the results of several landmark trials including intensive insulin therapy and activated protein C were not replicated in subsequent studies. The high rate of non-replication is a consequence of the ill-founded strategy of claiming conclusive research findings solely on the basis of one study whose  $p$  value  $< 0.05$ . The hesitancy to conclude the efficacy of a treatment based on a single trial may be especially true for studies that appear counterintuitive and question recent paradigms such as the routine use of neuromuscular blockade in critically ill patients. A second large randomized trial with positive results would elevate early neuromuscular blockade for ARDS to the highest GRADE level and the strongest recommendation based on modified Delphi methodology.

Reservations about the Papazian trial were based on the following concerns about study design, statistical analysis, and adverse event reporting.

1. Though the preplanned primary outcome was adjusted mortality, and the adjusted mortality rate was significantly different between the two groups ( $p = 0.04$ ), crude mortality was not significantly different between the groups ( $p = 0.08$ ).
2. The infusion of neuromuscular blockade occurred during the first 48 hours of the study. However, the Kaplan-Meier curves achieved separation after Day 12 in regard to the probability of achieving unassisted breathing, and after Day 18 in regard to mortality. The delay in the observed treatment effect raises concerns about the direct effects of neuromuscular blockade on the positive outcomes in the clinical trial.
3. Variables commonly used to assess the risk of ventilator induced lung injury, such as plateau pressure and tidal volume, were not different between the patients who received neuromuscular blockade and placebo, raising concerns about the biological plausibility of the therapy.
4. A low PEEP strategy was used in both arms of the Papazian trial. For patients with moderate to severe ARDS, meta-analyses suggest that high PEEP strategies may result in improved outcomes including mortality [15]. Based upon the likelihood that atelectrauma may be more common with lower PEEP strategy, neuromuscular blockade may have a different effect for patients receiving a high PEEP strategy.
5. All patients in the control arm of the Papazian trial received heavy sedation defined as a Ramsay score of six. The routine use of heavy sedation is associated with several deleterious outcomes including prolonged length of mechanical ventilation. Based on the results of our survey of PETAL investigators, 86% of respondents reported that the routine sedation goal for ARDS patients is not heavy sedation. Therefore, it is plausible that the positive results of the Papazian trial are related to the harmful and uncommon use of a heavy sedation strategy in the control arm.

6. Safety-related outcomes are commonly underreported in randomized controlled clinical trials resulting in misinterpretation and inadequate conclusions concerning the benefits of the intervention [16, 17]. The assessment of neuromuscular dysfunction was determined using only the MRC score to define weakness. In addition, the potential effects of neuromuscular blockade on the development of symptoms of post-traumatic stress disorder and paralysis recall were not determined. A better understanding of the long term risk associated with the use of neuromuscular blockade would allow clinicians to make a more informed decision about its utility in ARDS.
7. Based on the strength of the previous clinical trials and the need to replicate their results, we propose to test the safety and efficacy of a 48 hour infusion of neuromuscular blockade for reducing mortality in patients with early ARDS. *We hypothesize that early neuromuscular blockade will result in improved clinical outcomes, specifically hospital mortality prior to discharge home before day 90 in patients with moderate-severe ARDS.*

### 3.7 ROSE IS AN EARLY TREATMENT TRIAL

The goal of ROSE is to test early administration of neuromuscular blockade for 48 hours as close to the initial onset of moderate to severe ARDS as possible. All efforts will be made to emphasize very rapid enrollment as soon as this severity of ARDS is diagnosed. We believe early administration is crucial. Neuromuscular blockade is most likely to be effective in mediating lung injury and lung-injury induced non-pulmonary effects and inflammation, if administered early. In addition, though neuromuscular blockade is sporadically used in routine clinical practice, systematic early treatment is not widespread. Thus, if the null hypothesis of ROSE is rejected, this trial will significantly alter and improve current clinical care, leading to increased early treatment with neuromuscular blockade.

Our approach will be to leverage the new PETAL infrastructure and philosophy to screen and enroll patients early using a suite of techniques adapted from prior successful early intervention trials, including Emergency Department trials (Section 4.1). We will also monitor time from inclusion criteria being met to enrollment, overall and by site, and regularly discuss with sites strategies to encourage very early enrollment.

### 3.8 OBJECTIVES

#### **Primary Objective**

To assess the efficacy and safety of early neuromuscular blockade in reducing mortality and morbidity in patients with moderate-severe ARDS, in comparison to a control group with no routine early neuromuscular blockade.

#### **Primary Hypothesis**

Early neuromuscular blockade will improve mortality prior to discharge home before day 90, in patients with moderate-severe ARDS.

## 3.9 END POINTS

Analyses will be conducted on an intention to treat basis.

### 3.9.1 PRIMARY OUTCOME

The primary outcome is all-cause mortality prior to discharge home before day 90.

### 3.9.2 SECONDARY OUTCOMES

#### 1. ICU acquired weakness

- a. Manual muscle strength testing will be attempted at study day 7, and then every 7 days thereafter, until hospital discharge or day 28 (whichever comes first). Patients will be defined as having ICU acquired weakness if their Medical Research Council (MRC) score is < 48 (or mean MRC < 4 for each muscle group tested)[18, 19].
- b. Highest level of mobility will be assessed on study days 1-7 using the ICU Mobility Scale [20], and then every 7 days thereafter, until hospital discharge or day 28 (whichever comes first).

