## 5.1 EARLY NEUROMUSCULAR BLOCKADE GROUP

### 5.1.1 INITIATION AND DOSAGE

Study staff will ensure a Ramsay score of 5-6 (RASS of -4 to -5, or Riker of 1-2) is achieved and documented prior to initiation of neuromuscular blockade and that patients are receiving controlled modes of mechanical ventilation. We do not mandate sedative type or dose.

Initiation of neuromuscular blockade must begin within 4 hours of randomization. Patients randomized to the early neuromuscular blockade arm will receive a cisastracurium besylate bolus of 15 mg, followed by a continuous infusion of 37.5 mg/hour for 48 hours (Appendix J).

We chose this fixed, relatively high dosage for simplicity (train of four titration imperfect and with limited evidence base [24-26]) and to help ensure effective neuromuscular blockade (clinical observation and train of four monitoring can lead to under-dosing). This dosage is the same as used in the ACURASYS trial. We chose cisatracurium as its metabolism is independent of hepatic and renal function.

In the rare circumstance that neuromuscular blockage is deemed inadequate, (i) check the patient and the ventilator to confirm the correct reading, (ii) check the infusion rate and drug to confirm correct, (iii) rebolus, using the below recommendation and call the CCC for further direction as needed.

Recommendation: If the end-inspiratory plateau pressure remains greater than 32 cm of water for at least 10 minutes, it is recommended that the patient receive the administration of increasing doses of sedatives and decreasing tidal volume and positive end-expiratory pressure (if tolerated) before considering using open-labeled cisatracurium. If the treating physician still wants to administer a neuromuscular blocking agent, an open-label, rapid, intravenous injection of 20 mg of cisatracurium will be recommended for patients in the control or treatment arms of the study. If this rapid, intravenous injection results in a decrease of the end-inspiratory plateau pressure by less than 2 cm of water, a second injection of 20 mg of cisatracurium will be allowed. If after injection, the end-inspiratory plateau pressure does not decrease or decreases by less than 2 cm of water, cisatracurium boluses should not be administered again during the following 24-hour period.

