### 6.3.2 REFERENCE MEASUREMENTS

The following data will provide the basis for assessing protocol compliance and safety as well as between-group differences in several efficacy variables. Data for each of the variables will be recorded on the days shown in the Time-Events schedule (Appendix B) or until death, or discharge from the intensive care unit. Values will be derived from clinically available data.

1. NMB Dosing
  - a) Intervention Arm
    - i. Time and dose of loading dose
    - ii. Time of initiation of cisatracurium continuous infusion
    - iii. Reason and duration of infusion hold during first 48 hours
    - iv. Total dose of cisatracurium infusion during first 96 hours
    - v. Name and total dose of other NMB during first 96 hours
    - vi. Addition NMB administered after 96 hours (yes/no)
  - b) Control Arm
    - i. Name and total dose of any NMB used in the first 96 hours after randomization
    - ii. Addition NMB administered after 96 hours (yes/no)

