#### Reference Measurements (Daily)

The following parameters will be measured and recorded between 4:00 and 10:00 A.M. using the values closest to 8:00 A.M. on the days specified in the Time-Events schedule. The following conditions will be ensured prior to measurements: no endobronchial suctioning for 10 minutes; no invasive procedures or ventilator changes for 30 minutes. All vascular pressures will be zero-referenced to the mid-axillary line.

1. If receiving positive pressure ventilation: Ventilator mode, set rate, actual rate, minute ventilation, tidal volume, FiO2, PEEP, I:E ratio, plateau, peak, mean airway pressures, set peak flow, and set inspiratory time
2. PaO2, PaCO2, pH, and SpO2

Values for the following variables will be recorded for the dates shown in the Time-Events Schedule. If the measurements are not obtained during the 6-hour reference interval (4:00 to 10:00 A.M.), then the value obtained closest in time to the reference interval on the respective date will be recorded. If more than one value is obtained during the reference interval, then the value obtained closest to 8:00 A.M. will be recorded.

3. Rescue procedures used
  - a) Proning
  - b) Inhaled nitric oxide
  - c) Epoprostenol sodium
  - d) High frequency ventilation

- e) ECMO
- 4. Serum electrolytes and glucose
- 5. Administration of the following medication infusions:
  - a) Intravenous sedatives
  - b) Intravenous opioids
  - c) Enteral or intravenous corticosteroids ( $\geq$  20 methylprednisolone equivalents)
- 6. Sedation score: If RASS  $<$  -1 (or Riker  $<$  3, Ramsay  $>$  3), and sedation given, list reason given
- 7. Was a sedation interruption performed? Y/N
- 8. Modified SOFA
- 9. Fluid intake and output/CVP if available
- 10. ICU Mobility Scale: Score 0-10 (see Appendix M)

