### 2.4 On Study Variables

Variables that are measured daily, such as fluid balance, will be compared between treatment groups on each study day that they are measured.

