## Appendix A2: Reference Measurements

Variable	Category	Scale	Method
Time and dose of loading dose		Continuous	Descriptive
Time of initiation of cisatracurium infusion		Continuous	Descriptive
Reason and duration of infusion hold during first 48 hours		Binary>=48.5 hours Continuous	Descriptive
Total dose of cisatracurium infusion during first 96 hours		Continuous	Descriptive
Name and total dose of other NMB during first 96 hours		Dose, Continuous	Descriptive
Additional NMB administered after 96 hours (yes/no)		Binary	Descriptive
Name and total dose of any NMB used in the first 96 hours after randomization (Control Arm)		Binary (Yes/ No) Continuous (Total Dose)	Descriptive
Additional NMB administered after 96 hours (yes/no) (Control Arm)		Binary (Yes/ No) Continuous (Total Dose)	Descriptive

If receiving positive pressure ventilation: Ventilator mode		Categorical, Days 1-4 & 7	Monte Carlo Fisher's Exact Test
If receiving positive pressure ventilation: set rate actual rate minute ventilation tidal volume FiO 2 PEEP I:E ratio, plateau, peak, mean airway pressures set peak flow, set inspiratory time		Continuous, Days 1-4 & 7	T-Test
PaO 2 , PaCO 2 , pH, and SpO 2		Continuous, Days 1-4 & 7	T-Test
Serum electrolytes and glucose		Continuous, Days 1-4 & 7	T-Test
Intravenous sedatives Intravenous opioids Enteral or intravenous corticosteroids		Binary, Days 1-4 & 7	Chi-Square Test
Sedation score: If RASS < -1 (or Riker < 3, Ramsay > 3), and sedation given, list reason given		Reasons (Categorical) Scale Used (Categorical) Light/ Deep/ Agitation (Categorical) Mean score (Continuous)	Chi-square Test Chi-square Test Chi-square Test T-test
Was a sedation interruption performed? Y/N		Binary Daily	Chi-square Test

Fluid intake and output/CVP if available		Continuous	T-Test
ICU Mobility Scale	Safety	Binary (Able to sit at edge of bed or greater)	Fisher's Exact Test
Manual Muscle Testing	Safety	Continuous	T-test

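### Protocol 6.3.2 stops ICU Mobility Scale recording at ICU discharge, in conflict with 3.9.2 and Appendix B; the SAP should also name the tested mobility days and leave the infusion days untested

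*Protocol*

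**What the plan says.** **End of the window.** Protocol 3.9.2 item 1b, under ICU acquired weakness, scores the highest level reached: "mobility will be assessed on study days 1-7 using the ICU Mobility Scale [20], and then every 7 days thereafter, until hospital discharge". The window closes at day 28 if that comes earlier. Appendix B marks the scale as required on days 1-7, 14, 21 and 28, with no ICU limit on that row. Section 6.3.2 opens with a general rule: its variables are recorded on the days in Appendix B "or until death, or discharge from the intensive care unit". The scale is item 10 of the daily list under that rule, "ICU Mobility Scale: Score 0-10 (see Appendix M", with no end point of its own. Manual muscle testing, later in the same section, does have its own hospital-discharge end point.

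**Start of the window.** Section 5.1.1 starts blockade within 4 hours of randomization, with a bolus "followed by a continuous infusion of 37.5 mg/hour for 48 hours", after deep sedation. The day of randomization is study day 0, and Appendix B shows study blockade on days 0-2.

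**Analysis.** SAP 2.4 says daily variables "will be compared between treatment groups on each study day that they are measured". SAP Appendix A2 classes the scale as Safety, reduces it to "Binary (Able to sit at edge of bed or greater", and tests it by Fisher's exact test. That row names no days, although several other rows in the table specify days 1-4 and 7. SAP 2.3 tests at two-sided 0.05 without multiplicity correction.

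**The concern.** ICU discharge happens after randomization and depends on recovery. If recording stops there, a patient who improves and moves to the ward has no later score. Each weekly comparison is then made among those still in the ICU, and slower recovery in one arm shows as more patients remaining there, not necessarily as lower scores among them. SAP 2.7 analyses available data under a missing-at-random assumption and specifies nothing that would correct this.

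The risk that 6.3.2 is applied is not fanciful. SAP Appendix A3 treats SOFA after the ICU as normal. SOFA is item 8 of the same daily list, so the ICU limit does seem to have operated for at least one neighbour of the mobility item.

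Mobility matters here because Protocol 3.6 criticises the earlier trial for judging neuromuscular dysfunction by the MRC score alone, and the mobility scale is the other measure that 3.9.2 places under weakness. The awakening and comprehension screen in 6.3.2 is required for muscle testing but is not stated for mobility, so mobility can cover patients whom muscle testing misses.

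At the other end of the window, a Safety test on a day when one arm is paralysed by assignment mainly restates the assignment. It says little about acquired weakness.

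**Working it through.** The documents give no rate, power or sample size for mobility, so there is no stated figure to reproduce.

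**1. The end points side by side**

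| Source | Mobility recorded until |
|---|---|
| Protocol 3.9.2 item 1b | hospital discharge or day 28 |
| Protocol Appendix B | days 1-7, 14, 21, 28; no ICU limit on the row |
| Protocol 6.3.2, general rule with item 10 | scheduled days, or death or ICU discharge |
| SAP 2.4 and Appendix A2 | not stated |

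Two places agree, one conflicts, and the SAP does not settle it.

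**2. What an ICU-only comparison can hide (all rates assumed).** Suppose that by day 14, 50% of controls and 40% of active patients have left the ICU. Suppose also that in both arms 90% of ward patients and 20% of ICU patients can sit at the edge of the bed. Deaths are ignored.

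- Control, everyone: 0.5×0.9 + 0.5×0.2 = 0.55
- Active, everyone: 0.4×0.9 + 0.6×0.2 = 0.48
- ICU patients only: 0.20 versus 0.20

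A 7-point loss becomes zero. The exact zero follows from assuming equal rates within each location. The example shows the mechanism and does not predict its size.

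**3. How much of days 1 and 2 is under blockade.** Assume a randomization hour *r* uniform over day 0 and a start delay *d* of 0 to 4 hours. The infusion starts at *s* = *r* + *d* and ends at *s* + 48, in hours from the start of day 0. Day 1 is hours 24-48 and day 2 is hours 48-72.

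- Day 1: 99-100% of the time is blocked on average, and every active patient is blocked at 08:00 because *s* ≤ 28 < 32.
- Day 2, mean share blocked: E[min(*s*, 24)]/24. For *d* = 0 this is 12/24 = 50%. For *d* = 4 it is (280 + 96)/576 = 65%.
- Day 2, blocked at 08:00 (*s* ≥ 8): 16/24 = 67% for *d* = 0 and 20/24 = 83% for *d* = 4.
- Infusion running into day 3 (*r* > 24 − *d*): 0 for *d* = 0 and 4/24 = 17% for *d* = 4. So 83-100% of full infusions end during day 2.

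A paralysed patient scores 0 on the scale, and sitting over the edge of the bed is 3. On day 1 a score of 3 or more is therefore ruled out under the full infusion. On day 2 it is not, because the item records the highest level reached and most infusions end that day.

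**4. How readily the day-1 test turns significant (assumed control rates).** Take 704 per arm (1408/2; 1:1 allocation is assumed) and 0 active patients able to sit. Fisher's two-sided p is 0.062 with 5 controls able to sit and 0.031 with 6 (6/704 = 0.85%). The chance of six or more is 0.14 at a true control rate of 0.5%, 0.71 at 1% and 0.995 at 2%.

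If 0.2% of active patients can sit, with 680 per arm, the chance of p < 0.05 depends heavily on the control rate:

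| Controls able to sit | Probability of p < 0.05 |
|---|---|
| 0.5% | 0.04 |
| 1% | 0.34 |
| 2% | 0.90 |
| 3% | 0.99 |

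**5. Number of tests.** The schedule gives 7 + 3 = 10 mobility time points. Starting on day 3 leaves 5 + 3 = 8.

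**The case against.** The strongest reply on the end point is that the outcome definition and Appendix B already give the intended window. The sentence in 6.3.2 is generic, refers first to Appendix B, and cannot govern every item below it: rescue procedures are item 3 of the same list, yet are recorded through day 28. An Appendix B footnote about days 0-28 or study-hospital discharge has also lost its row marker in the text as read, so it may have applied to mobility. This stands as far as it goes. A reader might infer that the plan sets the wrong mobility window, and the documents do not support that. They show an unreconciled conflict in which the definition and the schedule agree. The conflict still matters, because 6.3.2 is the data-collection instruction and mobility has no end point of its own there.

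On the start, testing on days 1-2 is inferred from the general rule in SAP 2.4, since the mobility row names no days. Such a test would also be a valid intention-to-treat description of the two strategies. Both points are fair. A reader might further infer that active patients score 0 throughout day 2. They need not: most infusions end that day, and Protocol 5.1.3 allows earlier stopping. Nor do the documents justify withholding tests until day 4, since at most about 17% of infusions reach the first hours of day 3.

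On impact, SAP Appendix A3 defines ICU-acquired weakness by MRC score alone. Slower recovery would also show in ICU-free days, a secondary outcome, and disability is measured after discharge. This limits the damage. It does not make an ICU-only mobility comparison interpretable.

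**Conclusion.** The concern holds as a conflict within the protocol plus a gap in the SAP. Section 6.3.2 contradicts 3.9.2 item 1b and Appendix B on when mobility recording ends. Following it would restrict comparisons, once ICU discharges begin, to a group selected after randomization, and a real difference could be missed. How much would be missed is unknown; the 7-point example rests wholly on assumed rates.

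The secondary point holds fully for day 1 under the full infusion and partly for day 2, where 50-65% of the day is blocked on average. Whether the day-1 test would be significant depends on a control rate that the documents do not give: the probability ranges from 0.04 to 0.99 across the rates tabulated for 0.2% active. The overlap figures assume a uniform randomization hour and no early stopping.

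A reader might infer that the trial's weakness finding or its primary result is at risk. Neither is. What is affected is a supporting Safety measure, and the repair is nearly free, so it should be made.

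**What to change.** 1. **Protocol 6.3.2.** Exempt the ICU Mobility Scale from the ICU-discharge cut-off, so that it runs to hospital discharge or day 28 as in 3.9.2 and Appendix B. The appendix reference can be corrected in the same edit: item 10 points to Appendix M, but the scale is printed under a second Appendix L.
2. **SAP 2.4 and Appendix A2.** Name the tested mobility days. Show days 1 and 2 descriptively by arm, and test between arms on days 3-7, 14, 21 and 28.

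The cost is one sentence in each document. The ward scores, at most three weekly ones plus any days left up to day 7, are already planned in 3.9.2. The small downside is that mobility differences on days 1-2 are described and not tested.
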